4.3 Study Enrollment Procedures

Aim 1: Focus Groups

Identifying and recruiting trial participants: Participants will be identified and recruited through various organizations including Michigan Medicine entities (e.g., the CTSA recruitment portal, Pepper Center, and ADRC, UMHealthResearch), the Henry Ford Health System (HFHS), and community dementia organizations with which Drs. [name] and [name] have partnered with previously (Alzheimer's Association and Dementia Minds). Study staff will distribute flyers via mail and/or email to the organizations and individuals with mild cognitive impairment/early-stage dementia and care partners from an existing list of participants in our previous work who have indicated interest in being contacted again for future research to maximize exposure.

Anyone who thinks they may qualify for the study can call or email a study team member to inquire. Staff will use a screening log to document participant contact information and any reasons for ineligibility. The screening log will be stored on a RedCap (Research Electronic Data Capture) database. Focus groups will be virtual and conducted over Zoom. Each participant will receive the focus group questions and the brochure ahead of time. The virtual format will ensure a diverse sample and reduce participant burden. Following the group discussion, the study team will conduct brief follow-up phone interviews with select, individual focus group participants. The purpose of these follow-up phone calls is to allow participants and researchers time to reflect on the discussion and clarify any insights that emerged. Not all focus group participants will be asked to participate in a follow-up phone call.

Eligibility and Ineligibility criteria: Focus group PLWD participants will have no more than mild dementia based on the CP and/or PLWD self-report. Eligibility will be based on self-report and the dyad's availability and willingness to participate in the group discussion. Participation in the focus group will present no more than minimal risk to the participants and the probability of experiencing minimal risks associated with this project are not greater than risks encountered in daily life.

Consent procedures: Please see section 11 for consent procedures.

Aim 2: Pilot feasibility of (a) using the electronic health record (EHR) to identify PLWD experiencing CNS polyRx and (b) implementing the adapted EMPOWER intervention in two primary care clinics using pragmatic methods.

Identifying and recruiting trial participants: Patients in Aim 2 and 3 will not be recruited directly to participate.

Eligibility and Ineligibility criteria: We will use the electronic health record (EHR) to identify patients living with dementia prescribed these problematic medication combinations (2a). Team data analysts will use DataDirect—the portal for researchers into the Michigan Medicine and HFHS EHRs—to identify PLWD seen in primary care with CNS-active polyRx. ICD-10 codes will be used to identify PLWD (including MCI) with an ambulatory care encounter with a primary care clinician (internal medicine, family medicine, or geriatrics) during the preceding 12 months. Within each system, we will identify a pair of clinics that have relatively similar panel characteristics (similar volume overall; PLWD with similar distributions of gender, race/ethnicity) to serve as the paired intervention-control sites. Among PLWD, we will use current outpatient medications data to identify those with ≥ 3 active prescriptions of the medications that contribute to CNS polyRx (e.g., antidepressants, antipsychotics, anti-epileptics, benzodiazepines, non-benzodiazepine benzodiazepine receptor agonist hypnotics, or opioids). We will contact the primary care clinicians of eligible PLWD once by email to offer them the opportunity to exclude potential PLWD participants for whom they think the intervention would be inappropriate; clinicians will have one week to opt potential participants out, or to suggest an eligible patient we may have missed (if they do not reply, we will assume that we can proceed).

Randomization: We will randomly select one clinic (or more, as needed to meet the target dyad sample size) within each system as the intervention clinic; dyads in these clinics will receive the nudge intervention. Dyads within the other clinic in each system will serve as controls.

Consent procedures: We will request a waiver of informed consent for PLWD participants in Aim 2 and 3. See section 11.2 for details.

5 STUDY INTERVENTIONS

5.1 Interventions, Administration, and Duration

This project will adapt the EMPOWER educational brochure for PLWD receiving CNS polyRx. The educational brochure will be mailed to intervention participants identified through EHR at Michigan Medicine and Henry Ford Health System. Prior work utilizing the EMPOWER intervention specifically focused on sedative-hypnotic (e.g., benzodiazepines) deprescribing in older adults.¹⁵ In that EMPOWER trial, investigators developed an educational tool to “increase risk perception about benzodiazepines through knowledge acquisition and change in beliefs”¹⁶

(e.g., “*The dose that I am taking causes no side effects;*” [True/False]]); this tool (in the form of an 8-page brochure) was mailed to older adults on long-term benzodiazepine therapy. In the current study, this tool, to be delivered in the form of a brochure mailed to PLWD will describe what CNS polyRx is, present information about the associated risks, and suggest that they speak with their prescribing clinician or pharmacist about ways to potentially simplify their medication regimen. The tool will be adapted through three successive rounds of focus groups of PLWD and caregivers (n=5 PLWD-CP dyads per round for 15 dyads total). As part of Aim 2, we will identify eligible participants from the EHR and allow primary care clinicians to opt-out patients for whom they believe the intervention would be inappropriate. The educational tool will be mailed from the participating health systems with a cover letter from the respective clinic that includes the specific medication combination that made the PLWD eligible for the study. The goal of the educational nudge is to prompt a conversation with the PLWD’s clinician or pharmacist; the material will clearly state that individuals should not make any medication changes without discussing with their clinician. The EHR will be reviewed 4 months after the brochure is mailed to determine with there has been any change to the CNS polyRx.

5.2 Handling of Study Interventions

n/a

5.3 Concomitant Interventions

5.3.1 Allowed Interventions

All usual interventions are allowed.

5.3.2 Required Interventions

None.

5.3.3 Prohibited Interventions

None.

5.4 Adherence Assessment

n/a

6 STUDY PROCEDURES

6.1 Schedule of Evaluations

Assessment	Month 1-2	Month 3-4	Month 5-6	Month 7-8	Month 9-10	Month 11-12
Draft adapted tool	x					
Adapt content (focus groups x3)		x	x			
Follow-up phone calls		x	x			
Screen/Identify target PLWD in EHR			x			
Allow clinician opt-out of participants			x			
Clinic randomization			x			
Mailing of educational tool				x		
2-month chart review				x		
4-month chart review					x	
Clinician Interviews						x
Adverse Events				x	x	x

6.2 Description of Evaluations

6.2.1 Screening Evaluation

Aim 1: Screening for focus groups will be based on subject's self-reported diagnosis of early-stage dementia.

Aim 2/3: Screening for the intervention will occur through electronic health record (EHR) chart review, this project does not require screening evaluations.

Consenting Procedure

Aim 1: For the focus group discussions, the consent process will be interactive and allow the participants with dementia to express understanding and interest. Before the focus groups, participants will be mailed the adapted brochure for previewing and a simplified consent form with key information about the project and their involvement. At the beginning of the focus group, which will be conducted over the Zoom teleconferencing platform, study staff will review the main tenets of the Consent Information Sheet with all participants using a comprehensive oral script and take time to answer questions. Participants will also be informed that they may be asked to participate in a brief follow-up phone call after the focus group (scheduled no later than 2 weeks following the focus group, at the selected participant's convenience). At the beginning of the focus group when staff summarizes the Consent Information Sheet, participants will be informed that they can opt out of eligibility for the potential follow-up phone call.

Aims 2/3: For the intervention we will request waiver of informed consent for PLWD intervention participants; see section 11.2.

Screening

Aim 1: Screening for focus groups will be based on subject's (PLWD and/or CP)self-reported diagnosis of early-stage dementia.

Aims 2/3: Screening to identify eligible participants will occur through electronic health record (EHR) chart. We will provide primary care clinicians the opportunity to opt-out their patients if they think the intervention is not clinically appropriate. The confirmed PLWDs will be the recipient of the nudge intervention.

6.2.2 Enrollment, Baseline, and/or Randomization

Enrollment

Aim 1: Research staff will contact potential participants by telephone to collect basic demographic information to ensure a diverse sample and determine eligibility. Eligibility will be based on 1.) a diagnosis of dementia of any type with no more than mild dementia as reported by the PLWD and/or the care recipient and 2.) the dyad's availability and willingness to participate in the virtual group discussion.

Aim 2/3: Once a PLWD is deemed eligible based on chart review and mailed the educational tool, they are enrolled in the project.

Baseline Assessments

Aim 1: There are no baseline assessments for focus group participants.

Aim 2/3: There are no baseline assessments of the participants. Baseline information will be collected from the EHR, including basic demographics (age, gender, race/ethnicity), diagnoses, and active medications include CNS-active.

Randomization

Aim 1: n/a

Aim 2/3: We will randomly select one clinic (or more, as needed to meet the target sample size) within Michigan Medicine and Henry Ford Health System as the intervention clinics from which PLWD will receive the nudge intervention. PLWD within the other clinic in each system will serve as controls.

6.2.3 Follow-up Visits

Aim 1: Participants in the group discussion may be asked to participate in a follow-up phone call 1-2 weeks after the group discussion is over. The follow-up will allow time for researchers to reflect on the discussion and to clarify any questions that may come up after the discussion. Not every focus group participant will be asked to participate in a follow-up. After the research team reviews transcripts, the research team will clarify any questions that come up after the discussion is over. Additionally, based on the teams' previous experience in working with CP-PLWD dyads, some care participants may not be comfortable being frank with their PLWD present and the follow-up may allow care partners the opportunity to clarify anything without their PLWD present. The follow-up phone call will be brief (≤ 15 minutes) and not all participants will be asked to participate. Potential participants will be called or emailed after the focus group to determine if they are interested in participating and the call will be scheduled at their convenience.

The intervention does not entail any follow-up visits. For evidence of implementation feasibility, we will do a 2-month chart review of PLWD primary care and pharmacy notes to determine if there is documented evidence of conversation related to the medications of interest (i.e., did the nudge intervention have the intended outcome).

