1.2 Secondary Objectives

- Adapt an educational nudge intervention to help motivate CNS polyRx deprescribing among PLWD
- Establish mailing of the educational brochure within the clinic workflow by engaging clinicians and pharmacists at each of the identified clinics
- Establish implementation feasibility: after sending the tool, the proportion of enrollees with documentation in the EHR of discussion regarding CNS-active medications with a prescribing clinician (or pharmacist).

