6.2.4 Completion/Final Evaluation

We will repeat a final EHR review for evidence of documented conversation related to these medications. In addition, we will review the active medications to determine the primary outcome of changes to the CNS-active medication regimen.

Additionally, we will conduct informant interviews with 10 primary care clinicians across intervention clinics from U-M and HFHS. The purpose of these interviews will be to explore potential barriers with experts and will explore whether:

- PLWD discussed receiving the tool with the clinician;
- Clinician perception of whether the tool motivated:
 - discussion related to prescribing that might not have occurred otherwise;
 - prescribing changes that might not have occurred otherwise;

- Clinician suggestions for modifications to the tool;
- Clinician suggestions regarding their perceived barriers or facilitators to improving the appropriateness of CNS-active prescribing, e.g.:
 - Clinical uncertainty regarding which medications to address;
 - Lack of access to clinical pharmacists to facilitate medication changes;
 - Lack of psychosocial resources for the PLWD-CP dyad.

7 **SAFETY ASSESSMENTS**

7.1 **Specification of Safety Parameters**

n/a

7.2 **Methods and Timing for Assessing, Recording, and Analyzing Safety Parameters**

The intervention is presenting education, which has a benign safety profile. Should the participants, in consultation with their clinician, choose to make medication changes, then participants should be at *lower* risk of adverse events by minimizing the burden of these medications. In a recent study of deprescribing among PLWD (of any, not limited by medication class), there was no difference in hospitalization or mortality rates in intervention groups, and review of records did not “reveal any pattern of adverse drug withdrawal events associated with the intervention.”¹⁷ In the original EMPOWER intervention (deprescribing of sedative-hypnotics), “no major adverse effects requiring hospitalization were reported.”¹⁵

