9 STATISTICAL CONSIDERATIONS

9.1 General Design Issues

For this nudge intervention, the primary clinical outcome will be change in the total standardized daily dosage (TSDD) of the medication classes contributing to CNS polyRx as measured in the EHR, from baseline to 4 months after sending the adapted intervention. We hypothesize a decline in the total standardized daily dosage (TSDD) following the nudge intervention. The presumed mechanism of the intervention is that the nudge educational tool will activate the dyad to discuss their current medication regimen with the prescribing clinician or a pharmacist. To determine whether the intervention has had this desired effect, as an implementation feasibility target, the team at each site will revisit intervention PLWD charts to complete an expedited chart review. We will complete initial reviews approximately two months after sending the tool and final review four months after sending the tool.

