9.2 Sample Size and Randomization

Our goal of participants is a total of 120 PLWD (a total of 60 across 2 intervention clinics; 60 across 2 control clinics), after allowing for clinician opt-out. This will then allow us to obtain a reasonably precise estimate of the first feasibility outcome (i.e., documentation of a prescribing-related conversation in the EHR), allowing us to determine the number of clinics within each health care system needed for the future ePCT. We will also be able to estimate the lower limit of a 95% confidence interval around the implementation feasibility target (i.e., documented discussion regarding CNS polyRx) not to drop below the pre-determined target of 50%. With N=60 PLWD (i.e., the PLWD in the intervention clinics) and assuming 65% to 75% to show evidence of CNS-medication discussions, the lower limits of a 95% confidence interval for implementation

feasibility target will be 51.6% to 62.1%, respectively. Meeting the implementation feasibility target will allow us to proceed to a full ePCT.

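### The feasibility outcome counts a documented discussion with any prescribing clinician or pharmacist, but the only note source named is primary care and pharmacy, and no section says which review feeds the 50% target

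*Combined protocol and SAP*

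**What the plan says.** Section 1.2 (Secondary Objectives) defines implementation feasibility as "the proportion of enrollees with documentation in the EHR of discussion regarding CNS-active medications with a prescribing clinician (or pharmacist". The Précis and section 3 use the same definition. Under section 5.1 the brochure will "suggest that they speak with their prescribing clinician or pharmacist about ways to potentially simplify their medication regimen", and section 9.1 gives the same route as the presumed mechanism. None of these places restricts the prescriber to primary care.

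The notes to be read are named once, in section 6.2.3 (Follow-up Visits), as the evidence for implementation feasibility: "we will do a 2-month chart review of PLWD primary care and pharmacy notes to determine if there is documented evidence of conversation". Section 6.2.4 then says "We will repeat a final EHR review for evidence of documented conversation related to these medications", with no note type. Section 9.1 says that "the team at each site will revisit intervention PLWD charts to complete an expedited chart review" and adds: "We will complete initial reviews approximately two months after sending the tool and final review four months after sending the tool". It names no note type either.

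Section 9.2 requires that the lower 95% confidence limit not fall below 50%. With 60 intervention patients and an assumed 65% to 75%, it gives lower limits of 51.6% and 62.1%. It concludes: "Meeting the implementation feasibility target will allow us to proceed to a full ePCT". It does not say whether the 2-month review, the 4-month review or both together supply the numerator.

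**The concern.** The named source is narrower than the outcome it is meant to measure. Section 4.3 selects patients on three or more active CNS prescriptions in the outpatient medication list, whoever wrote them, and the qualifying classes include antipsychotics, anti-epileptics and opioids. A patient can therefore qualify on a drug managed outside primary care, discuss it with that prescriber, and leave no trace in the notes that 6.2.3 tells the reviewer to open.

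Two things are at stake. First, the proportion decides whether the 50% target is met, which is the condition that 9.2 attaches to proceeding, and 9.2 also uses it to set the number of clinics for the future trial. Second, the total standardized daily dosage in 9.5 adds up all active outpatient CNS prescriptions, so a dose reduction by another prescriber lowers the clinical outcome while the discussion behind it may be recorded as absent. The mechanism measure and the clinical outcome would then cover different prescribers.

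**Working it through.** **Inputs from section 9.2.** n = 60; assumed rates 65% and 75%; target: lower 95% limit not below 50%; stated lower limits 51.6% and 62.1%.

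**Step 1: reproduce the plan's figures.** The exact (Clopper-Pearson) lower limit for x of n is the 2.5% quantile of a Beta(x, n − x + 1) distribution.
- 65%: x = 0.65 × 60 = 39; Beta(39, 22) gives 51.6%.
- 75%: x = 0.75 × 60 = 45; Beta(45, 16) gives 62.1%.

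Both match. The Wald (52.9%, 64.0%) and Wilson (52.4%, 62.8%) limits do not, so the plan used the exact interval.

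**Step 2: the smallest passing count.** For 38/60 (63.3%), Beta(38, 23) gives 49.9%, which fails. For 39/60 the limit is 51.6%, which passes. The rule is therefore x ≥ 39.

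**Step 3: slack at each rate.** Expected count minus 39:
- 65%: 39 − 39 = 0
- 70%: 42 − 39 = 3
- 75%: 45 − 39 = 6

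**Step 4: illustration of the loss.** Let p be the true rate of documented discussions with any in-system prescriber or pharmacist. Let s be the share of those discussions that appear only in notes outside primary care and pharmacy. The documents give no value for s, so 0% to 15% is an assumption. The observed rate is p(1 − s), and the chance of passing is P(X ≥ 39) with X ~ Binomial(60, p(1 − s)). Patients are treated as independent, as in the plan's own interval.

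| True rate p | s = 0% | s = 5% | s = 10% | s = 15% |
|---|---|---|---|---|
| 65% | 56% | 35% | 19% | 8% |
| 70% | 84% | 65% | 43% | 23% |
| 75% | 97% | 89% | 71% | 48% |

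Example: p = 70% and s = 10% give an observed rate of 0.70 × 0.90 = 63%, and P(X ≥ 39) = 43%.

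**Step 5: direction.** Reading fewer note types cannot add a qualifying discussion; it can only miss one. Any bias from this cause is downward.

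**The case against.** A reader might infer that the 2-month review decides the 50% target and that every patient who turns to a specialist is counted as a failure. The documents do not say this. The note restriction is written for the 2-month review only. Section 6.2.4 speaks of an EHR review and 9.1 of a chart review, both without limits. Repeating the review suggests the same sources, but that is inference. No section links the target to a particular review, and there is no scoring rule for specialist contacts. A specialist discussion that is also recorded in a primary care or pharmacy note would count, and so would a conversation with a pharmacist, which the brochure equally invites.

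Primary care is also a sensible main source. Every patient found by the EHR search has had a primary care encounter in the preceding 12 months, the cover letter comes from the clinic, primary care clinicians screen the list, and the review is meant to be expedited. Nothing in the documents shows that discussions recorded only elsewhere are common.

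The probabilities in the table need care as well. Section 9.2 states its 65% to 75% as the rate that will show evidence of discussion. If that was set with the planned review in mind, the loss is already inside it, and subtracting it again counts it twice. At 65% the chance of passing is only 56% with no loss at all; that fragility comes from the sample size and the target, not from the note source.

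All of this limits the size of the claim. It does not remove the mismatch. If the final review uses the same notes, the outcome is measured too narrowly at both times. If it reads more, one outcome has two sources and the plan does not say which counts. Both readings need a correction.

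**Conclusion.** The mismatch between the outcome definition and the only stated note source stands, as does the silence on which review supplies the numerator. Under 6.2.3, discussions recorded only in another in-system prescriber's notes are missed, and the feasibility proportion can be biased only downward by this.

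The size is not known. What can be said firmly is that the pass mark is 39 of 60. One missed discussion at an expected count of 39 is enough to fail, whereas six can be absorbed at an expected count of 45. The fall from 84% to between 65% and 23% at a true rate of 70% is an illustration. It rests on an assumed 5% to 15% share, on independence between patients, and on 70% being the rate before any loss. The sample size and the stated confidence limits need no change.

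**What to change.** Settle the following before chart abstraction begins.

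- In 6.2.3, change the source to in-system EHR notes from primary care, pharmacy and any clinician listed at baseline as prescriber of a qualifying CNS medication.
- Add the same source to 6.2.4 and 9.1, which at present name none.
- In 9.2, state which review, or which combination of the two, supplies the numerator for the 50% target.
- Record the type of clinician for each discussion found, so that the proportion based on primary care and pharmacy notes alone can also be reported.

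If only primary care and pharmacy discussions were ever meant to count, the consistent alternative is to narrow the outcome definition in the Précis, 1.2 and section 3.

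The cost is protocol wording, one abstraction field, and some additional notes to open for about 60 intervention charts. Discussions with prescribers outside the two health systems would remain uncaptured, and this should be stated as a limitation.
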